4.1.3 Other efficacy variables

- Clinical remission (DAS28 of <2.6) by visit
- Low disease activity (DAS28 of \leq 3.2) by visit
- Proportion of patients achieving clinical response to treatment based on DAS28 reduction of ≥1.2 by visit
- Change from Baseline CDAI by visit
- Change in patient's arthritis pain as measured by Patient's Assessment of Arthritis Pain VAS by visit
- Change from Baseline in patient's fatigue as measured by Fatigue Assessment Scale by visit
- Change from Baseline in patient's physical function as measured by the HAQ-DI (Fries et al, 1980 and Lautenschläger et al, 1997) by visit
- Change from Baseline in health-related QoL measured as EQ-5D by visit, using the VAS part of the EQ-5D.
- Change from Baseline in quantity of concomitant DMARDs
- Change from Baseline in quantity of concomitant corticosteroids
- Incidence of discontinuation of CZP treatment due to DAS28 (CRP) remission
- Change from Baseline in duration of morning stiffness (in hours) by visit
- Change from Baseline in number of swollen and tender joints by visit (joint scores –TJC and SJC)
- Proportion of patients in clinical remission as defined by the ACR/EULAR 2011 remission criteria
- Employment status

- Employability due to RA
- Sick leave
- RA treatment following discontinuation of CZP

4.2 Safety variable

• Incidence of AEs

5 STUDY DESIGN

5.1 Study description

This is an observational, noninterventional, noncomparative, postauthorization safety study (PASS) to evaluate efficacy and long-term safety of CZP in adult patients with RA in need of treatment with a biologic.

The purpose of this study is to assess the clinical efficacy of CZP in achieving clinical remission with a DAS28 <2.6 after 2 years of therapy. The long-term safety will be evaluated, using reported treatment emergent adverse events.

The observational nature of the study leaves the therapeutic decision exclusively within the discretion of the treating physician. First the decision to treat the patient with CZP needs to be taken, before the treating physician can enroll the patient into this study. In addition, patient procedures and assessments will be performed in the frame of current standard clinical practice and as directed in the SmPC. Management of AEs will be handled according to drug safety regulations in Germany.

5.1.1 Study duration

The entire study duration per patient is intended to be 116 weeks if not prematurely discontinued (see Section 6.3 for withdrawal criteria).

Intervals of visits:

- Baseline Visit at onset of therapy (after deciding to treat the patient with CZP).
 Note: A patient may be enrolled into the study after the start of CZP treatment if he/she met all inclusion and exclusion criteria at the start of CZP treatment. Written data consent must be obtained no later than the start of Visit 2 and prior to conducting any clinical assessment at Visit 2. Following written data consent (ie, enrollment into the study), all relevant data from original records will be entered onto study-specific forms.
- Frequent visits are expected around Weeks 6, 12, 24, 36, 52, 64, 76, and 104: evaluation of efficacy and safety by the treating physician.
- Safety Follow-Up Visit around Week 116.

Patients who stop CZP for lack of efficacy or safety reasons will be followed up for 84 days to analyze which treatments were commonly used after treatment failure of CZP.

Patients who discontinue CZP treatment due to personal reasons or as a result of the treating physician's decision will also be followed up for 84 days (except for patients who withdraw consent and cannot be followed up further).

The end of the study is defined as the date of the last visit of the last patient in the study.

It is anticipated that this study will be conducted from Q3 2009 to Q4 2014.

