6 SELECTION AND WITHDRAWAL OF PATIENTS

6.1 Inclusion criteria

Patients must fulfill the following inclusion/exclusion criteria at the start of CZP treatment:

- 1. Before any data are collected on study-specific forms for a patient in this noninterventional PASS, written data consent will be properly executed and documented. The patient is informed and given ample time and opportunity to think about his/her participation and has given his/her written consent on the use of data. Note: A patient may be enrolled into the study after the start of CZP treatment if he/she met all inclusion and exclusion criteria at the start of CZP treatment. Written data consent must be obtained no later than the start of Visit 2 and prior to conducting any clinical assessment at Visit 2. Following written data consent (ie, enrollment into the study), all relevant data from original records will be entered onto study-specific forms.
- 2. Patient is considered reliable and capable of adhering to the observational plan (eg, able to understand and complete questionnaires, visit schedule, or medication administration according to the judgment of the treating physician.
- 3. Patient is male or female ≥18 years of age diagnosed with moderate to severe, active RA and is eligible for treatment with CZP therapy.
 Note: Patients enrolled into the study after the start of CZP treatment must have had a DAS28 score at the start of CZP treatment that is documented in their original records and indicates moderate to severe RA.
- 4. The decision to prescribe CZP has been made by the treating physician independently of his/her decision to include the patient in the study.
- 5. The patient's treatment must be within the terms of the SmPC.

Confidential Page 20 of 89

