10.1.1.2 Injection reactions

Injection reactions will also be recorded in the Noninterventional Observational Form. Injection reactions are classified as injection site reactions and systemic injection reactions.

An injection site reaction is any untoward medical event occurring at the injection site during or after study drug administration that can be at least possibly attributed to the study drug (ie, the relationship cannot be ruled out).

Examples: injection site pain, injection site burning, injection site erythema, injection site itching, injection site swelling.

A systemic injection reaction is any untoward medical hypersensitivity-like event other than injection site reaction, occurring during or after study drug administration that can be at least possibly attributed to the study drug. Systemic injection reactions are being further classified as acute and delayed based on timing and presentation of symptoms typical for hypersensitivity reactions.

Acute and delayed reactions to CZP should be reported according to the judgment of the Investigator, based on typical features, which include (but are not limited to) the following:

- 1. Acute injection reactions are usually defined as at least 1 of the following signs or symptoms occurring during or within 2 hours of the CZP infusion:
- Hypotension
- Urticaria
- Flushing
- Facial or hand edema
- Throat tightness, oral cavity or lip edema
- Headache
- Shortness of breath
- 2. Delayed injection reactions are usually defined as at least 2 of the following 4 signs or symptoms occurring within 1 to 14 days following the infusion:
- Rash
- Fever (more than 100°F [38°C])
- Polyarthralgias
- Myalgias

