12.1 Definition of analysis sets

The analysis set for the efficacy variables will be the Full Analysis Set. The Full Analysis Set is defined as all patients with a DAS28 ≥2.6 who took at least one dose of CZP and had at least one valid post-Baseline DAS28 value.

Note: the Full Analysis Set is defined in this way because patients who had a Baseline DAS28 value <2.6 would already be in remission. Therefore, the primary efficacy variable to reach clinical remission would not be defined.

The analysis set for the safety variables will be the Safety Set (SS), which is defined as all patients who took at least one dose of CZP.

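### Patients may be enrolled up to about Week 6 of CZP and are pooled with those consented at Visit 1, so early discontinuations and early AEs in the Safety Set are likely to be under-counted

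*Protocol*

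**What the plan says.** Section 5.1.1 places the Baseline Visit at onset of therapy but adds that "A patient may be enrolled into the study after the start of CZP treatment if he/she met all inclusion and exclusion criteria" when CZP was begun. The limit is "Written data consent must be obtained no later than the start of Visit 2 and prior to conducting any clinical assessment at Visit 2", and inclusion criterion 1 in Section 6.1 repeats it. Visit 2 falls at about Week 6: "Frequent visits are expected around Weeks 6, 12, 24, 36, 52, 64, 76, and 104". Footnote c to the schedule in Section 5.2 is narrower and puts consent for these patients at the start of Visit 2.

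Two conditions apply to late entrants. Criterion 3 in Section 6.1 requires that "Patients enrolled into the study after the start of CZP treatment must have had a DAS28 score at the start of CZP treatment", documented and indicating moderate to severe disease. After consent, "all relevant data from original records will be entered onto study-specific forms".

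Section 12 makes no distinction by entry route:

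- The Safety Set is one "which is defined as all patients who took at least one dose of CZP" (Section 12.1).
- The Full Analysis Set requires a DAS28 of at least 2.6, one dose and one valid post-Baseline DAS28 (Section 12.1).
- Baseline is Visit 1 in Week 0 for everyone (Section 12.2).
- Entry route is not among the subgroups in Section 12.3.1.

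The safety variable is the incidence of AEs (Section 4.2). Section 12.4.1 plans descriptive AE tables, separate tables for AEs leading to withdrawal, and a summary of injection reactions.

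**The concern.** A patient who enters late has to be in contact with the practice when consent is taken. Starters who died or left care before then are absent from this route, and the protocol has no register of starters that would show how many there were. For starters who stopped or reacted badly but stayed under care, the physician may already know the early course when deciding whether to offer enrolment. Criterion 4 in Section 6.1 makes the prescribing decision independent of the decision to include. It does not make inclusion independent of what happened after the first doses.

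This is left truncation combined with possible selection on early outcome. Time is counted from Week 0 for all patients, so the late route contributes weeks in which the worst early courses are missing or thinned out. Reactions to the first doses fall in that window: Section 10.1.1.2 describes acute reactions within 2 hours and delayed ones "occurring within 1 to 14 days following the infusion".

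The study is a single-arm postauthorization safety study meant to describe real-life use. There is no comparator in which the same bias could cancel, so it passes straight into the reported incidences.

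**Working it through.** **The plan's own figure.** Section 12.7 gives 1068 patients for a precision of ±3.0% at a 50% remission rate: 1.96² × 0.5 × 0.5 / 0.03² = 1067.1, rounded up to 1068. This reproduces. It describes sampling error in the remission rate only. It does not cover selection, and a larger sample would not reduce that. The protocol gives no figure for late entry or early stopping.

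**Inputs for the size of the effect.** None of these is in the protocol; all are assumptions.

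- f: share of enrolled patients who are late entrants, taken as 20%, 40% and 60%.
- e: share of CZP starters who stop before Visit 2, taken as 10% and equal in both routes.
- Share of late-route early stoppers who still consent: taken as none, which gives the largest bias.

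**Bound on the bias.** If no late entrant is an early stopper, the early-stop share seen in the pooled cohort is (1 − f) × e:

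- f = 20%: 0.8 × 10% = 8%
- f = 40%: 0.6 × 10% = 6%
- f = 60%: 0.4 × 10% = 4%

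**Same check with the share defined among starters.** Let s be the share of starters who would be consented only at Visit 2, and q their early-stop risk. If late-route stoppers never enrol, the share seen is (1 − s)q / (1 − sq). With s = 50% and q = 10%: 0.05 / 0.95 = 5.3% instead of 10%. Over s = 10% to 75% and q = 2% to 15%, the share seen runs from about 0.91 down to 0.25 times the true value.

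**Sensitivity to the strongest assumption.** Keep s = 50% and q = 10%, but let some late-route early stoppers consent:

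- half of them: (0.05 + 0.025) / (1 − 0.025) = 0.075 / 0.975 = 7.7%
- all of them: 10%, and this bias is gone.

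**Remission.** The first scheduled post-Baseline DAS28 components are at Visit 2 (Section 5.2). A patient who stops before then and has no later DAS28 leaves the Full Analysis Set by either route. With remission p among all starters and no remission among early stoppers, the Full Analysis Set rate is p / (1 − q) for patients consented at Visit 1 and for late entrants alike. Pooling them produces no difference.

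**The case against.** Four points deserve a fair hearing.

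1. *Early stoppers are not barred.* A reader might infer that anyone who stopped CZP or reacted badly before Visit 2 can never enter late. The text does not support that. Eligibility is judged at CZP start, consent may come before Visit 2 under Section 5.1.1, and nothing requires the patient to be on CZP at consent. Only death and loss to care exclude a patient outright. This stands, and it is why the figures above are bounds.

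2. *Early events are transcribed.* Original records are entered after consent, and the prompt in Section 10.1.2 asks about the period since the last visit. This recovers events in those who enrol, but not in those who never do. It is also true that the reaction windows in Section 10.1.1.2 apply to any administration over two years, so only the reactions to the first doses are at issue.

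3. *Remission.* A reader might infer that the primary remission rate is inflated by late entry. Since the Full Analysis Set already requires a post-Baseline DAS28, that does not follow. A difference would need early stoppers consented at Visit 1 to return for a DAS28 while comparable late-route stoppers did not consent, and the documents do not show this.

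4. *This is material for the SAP.* Table layouts are. However, the entry rule, the analysis sets and the subgroup list are fixed in this protocol, and no SAP can recover patients who were never registered.

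The reason given for late entry in Section 16.7 is practical: consent cannot always be obtained at Visit 1. It is a legitimate choice in a noninterventional study, and it offers no support for assuming that the late share is large.

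**Conclusion.** The point holds for safety. The protocol admits patients up to about six weeks after first dose, has no means of capturing starters lost before consent, and pools both routes from Week 0. Early discontinuation and early AE incidence in the Safety Set, including reactions to the first doses, should be expected to come out too low.

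The direction is an expectation, and the amount is unknown. The 8%, 6% and 4% against a true 10% rest on an assumed early-stop risk, an assumed late share, equal risk in both routes and no late-route stopper enrolling. They mark the upper end of the bias under those inputs. If every late-route stopper still under care consents, only deaths and losses to care remain missing. For the primary remission rate the effect is probably small, and no figure is claimed.

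**What to change.** In Section 12, add a flag for each patient: consented on or before the first CZP dose, or after it. The consent form is personally dated (Section 13.1). Section 9.16 lists who administers the drug and the missed doses but no first-dose date, so confirm that this date is captured.

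Then:

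- Report AE incidence, AEs leading to withdrawal, injection reactions and early discontinuation by this flag, beside the pooled result.
- Take the Week 0 to 6 safety estimates from patients consented at or before first dose.
- Show the primary remission rate by the same flag as a sensitivity analysis.
- Use delayed entry at the consent date only if person-time rates are reported. It does not suit the simple incidences now planned.

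The cost is one derived variable and a few extra tables, with less precision in the subset consented at start. No visit, procedure or treatment changes.

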5.1.2 Number of planned patients and sites

Physicians treating RA patients with biologics will be invited to participate in this PASS. Appropriate selection of the study sites will ensure collection of data representative for the general RA population.

The study will be conducted at approximately 160 sites in Germany. A total of 1068 patients are planned to be enrolled in this study, after the treating physician has made the decision to treat the patient with CZP.

Confidential Page 17 of 89

5.2 Schedule of study assessments

The schedule of study assessments by visit are presented below.

Assessments ^a	Treatment period ^b							Safety Follow -Up		
Visit	V1	V2	V3	V4	V5	V6	V7	V8	V9	V10
Week	0	6	12	24	36	52	64	76	104	116
Written Data Consent ^c	X	X								
Demographics / Medical History	X									
Presence of Rheumatoid Factor	X									
Presence of anti-cyclic citrullinated peptide antibodies	X									
RA history	X									
Concomitant Medication	X	X	X	X	X	X	X	X	X	X
Adverse Events		X	X	X	X	X	X	X	X	X
Drug administration	X	X	X	X	X	X	X	X	X	
Joint scores (TJC, SJC) (28 joint count)	X	X	X	X	X	X	X	X	X	
Acute phase reactant (CRP or ESR)	X	X	X	X	X	X	X	X	X	
Morning stiffness	X	X	X	X	X	X	X	X	X	
Patient's Global Assessment of Disease Activity (VAS)	X	X	X	X	X	X	X	X	X	
Physician's Global Assessment of Disease Activity (VAS)	X	X	X	X	X	X	X	X	X	

Confidential Page 18 of 89

Assessments ^a	Treatment period ^b							Safety Follow -Up		
Visit	V1	V2	V3	V4	V5	V6	V7	V8	V9	V10
Week	0	6	12	24	36	52	64	76	104	116
Arthritis pain VAS	X	X	X	X	X	X	X	X	X	
Fatigue Assessment Scale	X	X	X	X	X	X	X	X	X	
HAQ-DI	X	X	X	X	X	X	X	X	X	
EQ-5D	X	X	X	X	X	X	X	X	X	
Sick leave	X	X	X	X	X	X	X	X	X	
Employment status and employability due to RA	X	X	X	X	X	X	X	X	X	
Information on subsequent RA treatment										X

CRP=c-reactive protein; EQ-5D=Euro Quality of Life – 5Dimensions; ESR= erythrocyte sedimentation rate; HAQ-DI; Health Assessment Questionnaire-Disability Index; RA=rheumatoid arthritis; SJC=swollen joint count; TCJ=tender joint count; V=Visit; VAS=Visual Analogue Scale

Confidential Page 19 of 89

^a Only if assessed as per current clinical practice. Since this is a noninterventional study, no additional diagnostic or monitoring procedure will be applied.

b Visits are recommended to be quarterly.

Written data consent will be obtained before any data are collected on study-specific forms. Written data consent may be obtained after the start of CZP treatment if the patient met all inclusion and exclusion criteria at the start of CZP treatment. For these patients, written data consent must be obtained at the start of Visit 2 and prior to conducting any clinical assessment at this visit.

5.3 Rationale for study design and selection of dose

This is an observational, noninterventional, noncomparative, postauthorization study to determine the use of CZP in adult patients with RA who are eligible for treatment with CZP according to the SmPC. This study was designed to assess the efficacy and long-term safety of CZP after 2 years of therapy. The selection of the dose will be determined by the patient's prescribing physician and procedures will follow standard clinical practice as defined in the SmPC. Since the number of patients included in this noninterventional study will add significantly to the existing safety data for CZP, this study is a PASS.

This study was designed to assess the efficacy and long-term safety of CZP after 2 years of therapy in daily practice. The selection of the dose will be determined by the patient's prescribing physician.

Since study patients will receive CZP in accordance with the SmPC guidance, the risk for the patients is not considered to be increased by their participation in this noninterventional study.

6 SELECTION AND WITHDRAWAL OF PATIENTS

6.1 Inclusion criteria

Patients must fulfill the following inclusion/exclusion criteria at the start of CZP treatment:

- 1. Before any data are collected on study-specific forms for a patient in this noninterventional PASS, written data consent will be properly executed and documented. The patient is informed and given ample time and opportunity to think about his/her participation and has given his/her written consent on the use of data. Note: A patient may be enrolled into the study after the start of CZP treatment if he/she met all inclusion and exclusion criteria at the start of CZP treatment. Written data consent must be obtained no later than the start of Visit 2 and prior to conducting any clinical assessment at Visit 2. Following written data consent (ie, enrollment into the study), all relevant data from original records will be entered onto study-specific forms.
- 2. Patient is considered reliable and capable of adhering to the observational plan (eg, able to understand and complete questionnaires, visit schedule, or medication administration according to the judgment of the treating physician.
- 3. Patient is male or female ≥18 years of age diagnosed with moderate to severe, active RA and is eligible for treatment with CZP therapy.
 Note: Patients enrolled into the study after the start of CZP treatment must have had a DAS28 score at the start of CZP treatment that is documented in their original records and indicates moderate to severe RA.
- 4. The decision to prescribe CZP has been made by the treating physician independently of his/her decision to include the patient in the study.
- 5. The patient's treatment must be within the terms of the SmPC.

Confidential Page 20 of 89

6.2 Exclusion criteria

Patients are not permitted to enroll in the study if any of the following criteria is met:

- 1. Patient has previously (before Visit 1) been treated with CZP
- 2. Patient has known hypersensitivity to any components of CZP

6.3 Withdrawal criteria

Patients are free to withdraw from the study at any time without prejudice to their continued care.

If a patient discontinues for any reason, this reason must be recorded on the Study Completion Form. The physician will be encouraged to invite the patients who discontinue CZP therapy early to return to the clinic/practice for posttreatment. A Safety Follow-Up Visit will be performed 84 days after administration of the last dose of CZP.

In case a patient withdraws his/her data consent no further data should be collected or submitted on this patient or caregiver. If a patient is institutionalized, this should be recorded on the medical update form. Follow-up of hospitalized patients should continue during hospitalization. Hospitalization, by itself, does not necessarily constitute a reason for discontinuation.

The treating physician is free to add or withdraw any kind of medication, or to withdraw the patient from the study at his/her own discretion.

7 STUDY TREATMENTS

7.1 Description of medicinal products

Certolizumab pegol will be provided on prescription from the treating physician.

7.2 Treatments to be administered

Patients will self-administer or be administered commercially available CZP according to standard clinical practice for the prescribing physician and as defined by the SmPC.

7.3 Packaging

The commercially available drug of CZP will be used with the trademark Cimzia[®].

7.4 Labeling

Certolizumab pegol will be supplied as a commercially available product and as such will be labeled according to local requirements.

7.5 Handling and storage requirements

Certolizumab pegol will be provided upon prescription of the treating physician.

Certolizumab pegol must be stored in a refrigerator $(2^{\circ}C - 8^{\circ}C)$ and must not be frozen. The prefilled syringe must be kept in the outer carton in order to be protected from light.

The patient must be instructed to store CZP out of the reach and sight of children.

Confidential Page 21 of 89

The physician (or designee) will instruct the patient to store the medication following the instructions on the label.

